7.3.3 TREATMENT VISIT

- Greater than 30 days between baseline and treatment visits will require that the subject be re-screened to confirm enrollment eligibility.
- Obtain pregnancy screen (if applicable) prior to study treatment.
- Perform study treatment.
- Provide standard of care post-treatment instructions.

7.3.4 FOLLOW-UP

Subjects will be asked to return to the clinic for follow-up visits at 1, 3, 7-, 30-, 90-, and 180-days post-treatment, see **Table 6**. At all visits, subjects will be assessed for safety and pain, standardized images will be taken, adverse events and protocol deviations will be assessed. At D30, 90, and 180 visits, study outcome measures (GAIS, Laxity Tests) will be completed. At the 180-day follow-up appointment in addition to the above referenced assessments, the subject will complete a Patient Satisfaction Questionnaire.

7.3.5 UNSCHEDULED VISIT

Any unscheduled visit or examine should be documented in the subject's medical record and adverse event form (if applicable) stating the reason for the visit and any actions taken. The Sponsor should be notified of the unscheduled visit.

7.3.6 END OF STUDY (COMPLETION)

All subjects who have signed an Informed Consent Form will be considered enrolled in the study. Subjects who complete the study duration will be considered to have completed the study. The end of study will be defined as completion of all study visits by all enrolled subjects. If a device-related AE, SAE, or unanticipated serious device-related effect is ongoing at the final study visit, the subject will be followed until resolution, until the condition stabilizes, until the event is otherwise explained, or the subject is lost to follow-up.

A study closure visit may be conducted at the study site in order to review record retention requirements, device disposition requirements, etc., with site personnel. The Sponsor may choose to conduct the closure visit via telephone contact if appropriate.

8. ASSESSMENT OF SAFETY

8.1 SPECIFICATIONS OF SAFETY PARAMETERS

8.1.1 DEFINITION OF AN EXPECTED TREATMENT EFFECT (ETE) AND AN ADVERSE EVENT (AE)

An expected treatment effect is defined as any typical treatment side-effect of the Renuvion APR System of mild to moderate severity and lasting up to a typical maximum duration. An adverse event is defined as any new medical problem, or exacerbation of an existing problem, experienced by a subject while enrolled in the study, whether or not it is considered device-related by the investigator.

An **adverse event** (AE) is any untoward or unfavorable medical occurrence in a human subject, including any abnormal sign (for example, abnormal physical exam or laboratory finding), symptom, or disease temporally associated with the subject's participation in the research, whether or not considered related to the subject's participation in the research.

Apyx Medical Corporation

Protocol Number: APX-22-04-GR

Effective Date: October 2, 2023

Revision No: 04

Title: A Post-Market Study in Greece of a Minimally Invasive Lower Eyelid Treatment Utilizing the Renuvion System Clinical Trial Protocol

A preexisting condition (one that is present at the start of the study) will be recorded as an AE only if the frequency, intensity, or the character of the condition worsens during the study period. Neither the condition, hospitalization, prolonged hospitalization, nor surgery are reported as an AE in the following circumstances: hospitalization or prolonged hospitalization for diagnostic or elective surgical procedures for a preexisting condition. Surgery should not be reported as an outcome of an AE if the purpose of the surgery was elective or diagnostic and the outcome was uneventful.

All ETEs and AEs will be collected during the conduct of this trial.

8.1.2 DEFINITION OF SERIOUS ADVERSE EVENT (SAE)

Each adverse event should be assessed for its seriousness. The definition below should be used for this assessment. Please note that the term serious adverse event is not synonymous with a “severe” adverse event, which may be used to describe the intensity of an event experienced by the subject. (Please refer to **Section 8.2.1** for severity definitions.)

An adverse event should be classified as serious if it meets any of the following criteria:

- a. Death
Death was an outcome of the adverse event.
- b. Life-threatening
The subject was at substantial risk of dying at the time of the adverse event or use or continued use of the device.
- c. Hospitalization (initial or prolonged)
Admission to the hospital or prolongation of hospitalization was a result of the adverse event.
- d. Disability or Permanent Damage
The adverse event resulted in a substantial disruption of a person's ability to conduct normal life functions, i.e., the adverse event resulted in a significant, persistent or permanent change, impairment, damage or disruption in the patient's body function/structure, physical activities and/or quality of life.
- e. Congenital Anomaly/Birth Defect
Exposure to a medical product prior to conception or during pregnancy may have resulted in an adverse outcome in the child.
- f. Required Intervention to Prevent Permanent Impairment or Damage (Devices)
Medical or surgical intervention was necessary to preclude permanent impairment of a body function, or prevent permanent damage to a body structure, either situation suspected to be due to the use of a medical product.
- g. Other Serious (Important Medical Events)
The event does not fit the other outcomes, but the event may jeopardize the subject and may require medical or surgical intervention (treatment) to prevent one of the other outcomes.

Non-serious adverse events are all events that do not meet the criteria for a “serious” adverse event.

8.1.3 DEFINITION OF UNANTICIPATED ADVERSE DEVICE EFFECTS (EVENTS)

An unanticipated adverse device effect is defined as “any serious adverse effect on health or safety, or any life-threatening problem, or death caused by, or associated with, a device; if that effect, problem, or death was not previously identified in nature, severity, or degree of incidence in the investigational plan, or application (including

Apyx Medical Corporation

Protocol Number: APX-22-04-GR

Effective Date: October 2, 2023

Revision No: 04

Title: A Post-Market Study in Greece of a Minimally Invasive Lower Eyelid Treatment Utilizing the Renuvion System Clinical Trial Protocol

supplementary application), or any other unanticipated serious problem associated with a device that relates to the rights, safety, or welfare of subjects."

8.2 CLASSIFICATION OF AN EVENT

8.2.1 SEVERITY OF EVENT

Each adverse event should be assessed for its severity, or the intensity of an event experienced by the subject, using the following classifications:

- **Mild:** easily tolerated by the subject, causing minimal discomfort, and not interfering with everyday activities. These events generally do not require treatment.
- **Moderate:** sufficiently discomforting to interfere with normal everyday activities. These events are usually relieved by simple therapeutic measures.
- **Severe:** prevents normal, everyday activities. These events may require systemic drug therapy or other medical treatment.

8.2.2 RELATIONSHIP TO THE STUDY DEVICE AND PROCEDURE

The relationship to the study device and/or procedure and non-related events will be determined by the investigator utilizing the following categories:

- **Not Related:** An event for which an alternative explanation is conclusively identified – e.g., concomitant drug(s), concomitant disease(s), and/or the relationship in time suggests that a causal relationship is highly unlikely.
- **Related:** The adverse event follows a reasonable temporal sequence related to treatment by the device and/or study procedure, follows a known or suspected response pattern and a plausible alternative etiology cannot be identified.
- **Undetermined:** The relation of the adverse event has some temporal relationship to the device and/or study procedure, is not clearly due to another condition and the involvement of the study device and/or study procedure is unknown.

8.3 TIME PERIOD AND FREQUENCY FOR EVENT ASSESSMENT AND FOLLOW-UP

The occurrence of an AE or SAE may come to the attention of study personnel during a study visit or upon review by a study monitor. All ETEs and AEs will be captured on the appropriate CRF. Information to be collected includes event description, date of onset, clinician's assessment of seriousness and severity, relationship to study device/treatment (assessed only by those with the training and authority to make a determination), actions taken, and date of event resolution. All AEs occurring while on study must be documented appropriately regardless of relationship. All ETEs/AEs assessed as "not yet resolved" must continue to be followed via telephone contact, email or clinic visit every 7 days or sooner as per the physician's direction until event resolution or stabilization.

A pre-existing condition should not be reported as an adverse event unless there has been a substantial increase in severity or frequency of the problem that has not been attributed to natural history. Changes in the severity of an event will be documented to allow for a determination if the event should be re-categorized from an ETE to AE.

Safety evaluations for this study include an interview with the study subject at each follow-up visit by the Investigator or delegated study staff to elicit information about any medical occurrence that meets the definition of Adverse Event. This information will be documented in CRF without regard for cause or relation to device and/or procedure.

Apyx Medical Corporation

Protocol Number: APX-22-04-GR

Effective Date: October 2, 2023

Revision No: 04

Title: A Post-Market Study in Greece of a Minimally Invasive Lower Eyelid Treatment Utilizing the Renuvion System Clinical Trial Protocol

In addition, study subjects will be instructed in the Informed Consent Form, post-procedure take-home instructions, and verbally by study staff to report all complications experienced post study procedure to the site personnel as soon as they occur/are observed. Study staff will ensure that monitoring and management of all adverse events is prioritized. Subjects may be asked to come into the site at any time to assess adverse events.

Study investigators are provided liberty to mitigate adverse events as deemed necessary per ICH GCP Guidelines E6(R2)4.3.2 which states, "During and following a subject's participation in a trial, the investigator/institution should ensure that adequate medical care is provided to a subject for any adverse events related to the trial".

Adverse event resolution dates will be determined by investigator using either in-person or remote (phone, video call, text, email, etc.) examinations or communication with the subject. To ensure the most accurate reporting of adverse event durations, investigators are instructed not to wait until scheduled office follow-up visits to assess resolution.

It is the Investigator's responsibility to determine seriousness, severity, and relatedness of the Adverse Event to the device and procedure using the definitions in this protocol.

The PI will record all reportable events with start dates occurring any time after informed consent is obtained until 7 (for non-serious AEs) or 30 days (for SAEs) after the last day of study participation. At each study visit, the investigator will inquire about the occurrence of ETEs/AEs/SAEs since the last visit. Events will be followed for outcome information until resolution or stabilization.

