Recently, the use of thermal-induced collagen/tissue contraction has been expanded to minimally invasive procedures. Laser-assisted lipolysis (LAL) and radiofrequency-assisted lipolysis (RFAL) devices have combined the removal of subcutaneous fat with soft tissue heating to reduce the skin laxity that often results from fat volume removal. These devices are placed in the same subcutaneous tissue plane as a standard suction-assisted lipolysis (SAL) cannula and are used to deliver thermal energy to coagulate the subcutaneous tissue including the underside of the dermis, the fascia, and the septal connective tissue. The coagulation of the subcutaneous tissue results in collagen/tissue contraction that reduces skin laxity.

Laxity of the skin is part of the normal aging process, which results in characteristic changes in the skin and underlying connective tissue of the face. Aging is both intrinsic, an inevitable physiological process, and extrinsic, caused by external environmental factors such as air pollution and sun exposure¹². Aging processes create phenotypic changes in cutaneous cells as well as structural and functional changes in extracellular matrix components such as collagens, elastin, and proteoglycans which provide tensile strength, elasticity, and hydration to the skin¹². The result of aging is biologic changes to the skin, which include thin, dry skin, fine wrinkles, gradual dermal atrophy, loss of elasticity, and laxity¹². Specifically, lower eyelid blepharoplasty is a common surgical technique for addressing the undesirable progression of the aging lower eyelids, specifically lower eyelid wrinkles and skin redundancy¹⁹. This study is utilizing a minimally invasive technique to address the same items of concern.

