4.3.2 PRIMARY SAFETY ENDPOINT

The primary safety endpoint is an analysis of adverse events through the D180 post-treatment visit.

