8.4 REPORTING PROCEDURES

8.4.1 ADVERSE EVENT REPORTING

All Adverse Events (AEs) and Expected Treatment Effects (ETEs) observed by study subjects, investigators, or other study staff from first exposure to the study product through last study follow-up visit will be recorded. If a device-related AE, ETE, SAE, or unanticipated serious device related effect is ongoing at the final study visit, the subject will be followed until resolution, until the condition stabilizes, until the event is otherwise explained, or the subject is lost to follow-up. The investigator should make every effort to ensure that follow-up includes any supplemental investigations as may be indicated to elucidate, as completely as practical, the nature and/or causality of the AE or SAE. This may include unscheduled follow up visits for AE assessment.

Study subjects will be instructed in the ICF, post-treatment take home instructions, and verbally by study staff to report all AEs to the clinical study staff. AE information will be collected throughout the duration of the study and recorded on CRFs. Subjects experiencing ongoing adverse events will be contacted as per **Section 8.1**.

Any new medical problem, or an exacerbation of an existing condition, reported from the time the informed consent form is signed must be followed until the last study visit after the last study treatment or until event resolution.

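### Sections 8.1.1 and 8.3 conflict on when worsening of a pre-existing condition is an adverse event, and 8.3 filters on cause before anything is recorded

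*Combined protocol and SAP*

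**What the plan says.** Section 8.1.1 deals with pre-existing conditions twice. Its general definition of an AE takes in any "exacerbation of an existing problem, experienced by a subject while enrolled in the study, whether or not it is considered device-related by the investigator". Its specific sentence says that a condition present at the start "will be recorded as an AE only if the frequency, intensity, or the character of the condition worsens during the study period".

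Section 8.3 returns to the subject with a different rule: a pre-existing condition is not to be reported as an AE "unless there has been a substantial increase in severity or frequency of the problem that has not been attributed to natural history". The same section also states that "All AEs occurring while on study must be documented appropriately regardless of relationship" and, of the interview at each follow-up visit, that "This information will be documented in CRF without regard for cause or relation to device and/or procedure".

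Section 8.4.1 uses the broad form: any new problem, or "an exacerbation of an existing condition, reported from the time the informed consent form is signed must be followed".

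The events so classified feed Section 4.3.2: "The primary safety endpoint is an analysis of adverse events through the D180 post-treatment visit".

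**The concern.** Two staff members working from different sections could code the same worsening in opposite ways, and both would be following the protocol. The natural-history clause matters most, because it puts a causality assessment ahead of recording. Section 8.2.2 already has a place for that assessment and sets standards for it: Not Related needs a conclusively identified alternative or a timing that makes causality highly unlikely, and doubtful cases go to Undetermined. Section 8.3 sets no standard for attributing a change to natural history. A worsening that 8.2.2 would hold as Undetermined can therefore go unrecorded under 8.3.

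The wording has more effect here than in most trials, because the condition being treated is itself pre-existing. Entry requires a complaint of laxity or lines in the lower lid (Section 5.2), and Section 2.1 supplies a ready natural-history explanation: "Laxity of the skin is part of the normal aging process". The study has one arm, so there is no comparison against which such an attribution could be tested. At stake is the content of the primary safety endpoint.

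**Working it through.** The plan states no figure on this point, so there is none to reproduce. The check compares the two rules case by case and then gives a scale.

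**Step 1. Elements of each rule.**

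| Element | 8.1.1 | 8.3 |
|---|---|---|
| Size of worsening | no threshold | substantial, not defined |
| Dimensions | frequency, intensity, character | severity, frequency |
| Cause | irrelevant | excluded if attributed to natural history |

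The specific sentence in 8.1.1 is phrased as a necessary condition (only if). That a worsening is enough to count comes from the general definition in the same section, which includes exacerbation whether or not it is device-related.

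**Step 2. Apply both rules to each case.**

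| Case | 8.1.1 | 8.3 |
|---|---|---|
| Present at baseline, unchanged | no AE | no AE |
| Present at baseline, modest increase in intensity | AE | not reported |
| Present at baseline, change in character only | AE | not reported |
| Present at baseline, substantial increase, attributed to natural history | AE | not reported |
| Present at baseline, substantial increase, not so attributed | AE | AE |
| Absent at baseline, new after treatment | AE | AE (the sentence does not apply) |

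Every worsening reportable under 8.3 is also an AE under 8.1.1, and three kinds of worsening are AEs under 8.1.1 only. Using 8.3 in place of 8.1.1 can therefore lower the AE count but cannot raise it.

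**Step 3. Who makes the attribution.** Section 8.3 is written in the passive and names nobody for the natural-history attribution. Later in the same section the investigator is made responsible for seriousness, severity and relatedness. The Brief Study Overview in the Synopsis says that only the principal investigator treats. That the operator makes the attribution is an inference from these two statements.

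**Step 4. Scale.** Section 10.2 gives up to 16 treated subjects. If the AE result is summarised as the proportion of subjects with at least one AE (an assumption, since the plan defines no such rate), one omitted subject with no other AE changes it by 1/16 = 6.25 points. The documents do not say how many subjects might worsen. For an assumed range of 0 to 2 subjects, with exact (Clopper-Pearson) 95% intervals:

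- 0/16 = 0% (0 to 20.59%)
- 1/16 = 6.25% (0.16 to 30.23%)
- 2/16 = 12.5% (1.55 to 38.35%)

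The intervals are wide beside a shift of one subject, but they describe chance error. The omission would work in one direction only.

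**The case against.** The strongest reply is that this is a wording conflict in a small, descriptive, uncontrolled study. There is no safety hypothesis, and the halting rules in 8.5 contain no numerical threshold that a missing event could reverse. That stands, and it limits the severity. Several stronger readings are also tempting, and the documents do not support them.

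- **That every subject is affected.** Entry is for laxity or lines, and no minimum laxity grade is required. A subject who enters for lines with a snap-back Grade 0 has no documented lid laxity, so a later rise is a new problem that the 8.3 sentence does not touch.
- **That 8.3 contradicts its own statements on relationship and cause.** Those statements cover events that already meet the AE definition. The pre-existing-condition sentence decides what becomes an AE, so they neither contradict it nor cancel it.
- **That worsening would vanish from the study.** All three laxity grades are analysed as change from baseline at D30, D90 and D180 (Section 4.3.3). Investigator and subject GAIS each have three levels of worsening (Section 4.3.4.5). The possible loss is from the AE tabulation only.
- **That the AE rate falls by a known amount.** The 6.25 points apply only to a subject with no other AE. Moderate and severe pain are AEs in their own right (Section 4.3.4.7), so that cannot be taken for granted.
- **That any rise in a laxity grade should be an AE.** The medial grades rest on approximate millimetre values, the lateral bands share the 4 mm boundary, and no repeat measurement is specified. Three tests at three visits give 3 × 3 = 9 occasions per subject on which measurement noise could become an AE. Such a rule is a separate design choice and is not needed to remove the conflict.

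What remains is the conflict itself: three sections, two rules, and no statement of which prevails.

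**Conclusion.** The concern holds as a conflict between Sections 8.1.1 and 8.3, with 8.4.1 on the side of 8.1.1. It should be fixed, but it is not a critical defect. For subjects whose worsened lid feature was present at baseline, worsening after treatment could be attributed to aging and kept out of the primary safety endpoint. The direction is certain: compared with 8.1.1, the 8.3 rule can only reduce AE counts. Whether any event would actually be lost, and how many, cannot be determined from the documents. The lack of a control arm and the inferred overlap of operator and assessor make a natural-history attribution hard to check, but they do not show that it would be misused.

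**What to change.** Reconcile Sections 8.1.1, 8.3 and 8.4.1 to one rule. Replace the pre-existing-condition sentence in 8.3 with a reference to 8.1.1. State that an opinion that the change reflects natural history is entered in the relationship field under the categories of 8.2.2, and is not used to decide whether the event is recorded. Leave the laxity grades as additional outcomes, and do not make a grade rise an AE automatically.

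The cost is one sentence in a protocol amendment and matching instructions to the site, with no new visits or measurements. Reported AE counts may rise, and some of the added events will be classed as not related or undetermined.

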8.4 REPORTING PROCEDURES

8.4.1 ADVERSE EVENT REPORTING

All Adverse Events (AEs) and Expected Treatment Effects (ETEs) observed by study subjects, investigators, or other study staff from first exposure to the study product through last study follow-up visit will be recorded. If a device-related AE, ETE, SAE, or unanticipated serious device related effect is ongoing at the final study visit, the subject will be followed until resolution, until the condition stabilizes, until the event is otherwise explained, or the subject is lost to follow-up. The investigator should make every effort to ensure that follow-up includes any supplemental investigations as may be indicated to elucidate, as completely as practical, the nature and/or causality of the AE or SAE. This may include unscheduled follow up visits for AE assessment.

Study subjects will be instructed in the ICF, post-treatment take home instructions, and verbally by study staff to report all AEs to the clinical study staff. AE information will be collected throughout the duration of the study and recorded on CRFs. Subjects experiencing ongoing adverse events will be contacted as per **Section 8.1**.

Any new medical problem, or an exacerbation of an existing condition, reported from the time the informed consent form is signed must be followed until the last study visit after the last study treatment or until event resolution.

